7.2 Setting

This study will include the collection of data from multiple institutions in urology, medical oncology, etc. Plans are for patient recruitment to begin in 1Q2020, and continue for approximately 1 year, and data collection will be completed in 1Q2022.

7.2.1 Study Population and Eligibility Criteria

Japanese patients with radically unresectable or metastatic RCC treated with pembrolizumab in combination with axitinib will be eligible for study participation. Given the rare nature of RCC in pediatric patients, it is expected that most study participants will be adult patients. There are no exclusion criteria for this study.

The study will enroll approximately 200 patients with evidence of at least one dose of pembrolizumab plus axitinib at baseline, assuming that approximately 25% of patients will be excluded from the analysis population given missing or incomplete data on safety outcomes. The goal is to analyze data on approximately 150 advanced RCC patients treated with pembrolizumab plus axitinib.

7.2.2 Patient Withdrawal

Patients have the right to withdraw from the study at any time, without prejudice to their medical care, and without giving a reason. Any withdrawal must be fully documented in the case report form (CRF) and source documents. Discontinuation from the study for any other reasons (e.g., death) must be documented in the CRF.

VEAP ID NO: 9069

7.3 Variables

7.3.1 Exposure

The study is non-interventional and there is no assignment of drug. Patients receiving pembrolizumab in combination with axitinib as part of their routinely administered healthcare and consent to study participation will be followed. The study does not include collection of data on any comparator drug or drug combination. Information on pembrolizumab and axitinib exposure (e.g. date of first dose, dose, date of dose interruption/change, discontinuation and reason for discontinuation) will be collected via survey from HCPs. The Iyakuhinmei Data File (IDF) coding system, which is used in Japan when reporting medication safety data to PMDA, will be used.

It is anticipated that the treating physicians will treat patients in accordance with the local health authority approved product information as well as local treatment guidelines. In accordance with the approved Japanese product circular, the recommended dose of pembrolizumab for adults is 200 mg administered as an intravenous infusion over 30 minutes every 3 weeks. As such, although it is not dictated per protocol, it is anticipated that patients will have clinic visits with their HCP approximately every 3 weeks.

It is assumed that HCPs will complete the survey/electronic CRFs at the end of the observational study period (9 months) with data transcribed from the patient's medical records; although, there will be no source data validation of exposure data for this study. When hepatic AEs occur, investigators will be instructed to report the minimal information required for AE reporting via the EDC system per the AE reporting guidelines outlined in Section 9 of this protocol.

7.3.2 Outcomes

Health outcomes of interest include hepatic adverse clinical events and other abnormal changes in laboratory values related to liver dysfunction, such as aspartate aminotransferase (AST), alanine aminotransferase (ALT), GGT (gamma glutamyltransferase), total bilirubin, ALP (alkaline phosphatase). Hepatic adverse events will be coded using the Japanese version of the Medical Dictionary for Regulatory Activities (MedDRA). Data captured will include the absence or presence of the event, grade based on CTCAE v5.0-JCOG (common terminology criteria for adverse events v5.0-Japanese Clinical Oncology Group), the date of the outcome, interruption date or discontinuation date of pembrolizumab and/or axitinib, treatment for the AE (e.g. corticosteroids, other therapies), whether there is improvement after discontinuation or interruption of therapy (dechallenge), information related to rechallenge (when conducted by the investigator), laboratory values related to the AEs, and causal relationship of pembrolizumab and/or axitinib as assessed by the local HCP. If there are multiple hepatic adverse events, each should be reported separately.

It is assumed that HCPs will complete the survey/electronic CRFs at the end of the observational study period (9 months) with data transcribed from the patient's medical records; although, there will be no SDV of outcomes data for this study.

Protocol/Amendment No.: 3475-A97/000

VEAP ID NO: 9069

7.3.3 Covariates

The HCPs will be asked to record this information in the electronic CRFs. As for exposure and outcomes, there will be no SDV using medical records of any of the following covariate data.

Baseline demographic and clinical characteristics (prior to the index date)

• patient identification number †,

- gender,
- birth date (or age at the start of treatment),
- inpatient/outpatient category,
- reason for use of the index drug,
- pregnancy status (female only),
- height, weight,
- presence or absence of allergy history and content,
- presence or absence of smoking history and content,
- drinking habits, amount of drinking per day,
- presence or absence of medical history and details,
- presence or absence of viral hepatitis,
- presence or absence of history of drug-induced liver dysfunction (including immunotherapy-induced liver dysfunction)
- prior history of RCC (date of diagnosis, onset information, IMDC risk, type of disease, stage of disease, and metastasis) and RCC treatment (e.g. surgical treatment, radiotherapy, chemotherapy, immunotherapy)
- Karnofsky performance status
- presence or absence of complications and details,
- Child-Pugh classification

†: A unique number or symbol by which the physician can identify the case

Protocol/Amendment No.: 3475-A97/000

VEAP ID NO: 9069

Concomitant therapy (post-index date)

• name of concomitant therapy[surgical procedure, radiation therapy, concomitant drugs (only for patients with reported hepatic AEs)],

- duration or date of treatment,
- total dose of radiation (for radiation therapy)

7.4 Data Sources

Study-specific CRFs will be completed by HCPs and submitted using an electronic data capture (EDC) system. It is assumed that patient data will be sourced from the patient's medical records, but there will not be independent source data verification of the data submitted by each site.

In the registration form/CRF, the site will enter a unique number (patient identifier), which only the treating investigator and/or authorized personnel will be able to use to identify the patient. Common to all CRFs for the patient will be a case registration number, which will be used by the MAH to manage the cases.

The MAH will be the controller of data collected from the clinical sites. The MAH, as data controller, will take appropriate steps to ensure that personal data are protected. Data management and handling procedures will be developed for the study, and will mainly cover EDC system construction and organization for survey implementation, registration/CRF related activities (e.g. procedures of system linkage with other systems, ID issuance of the EDC system, workflow after registration and receiving CRF, query creation, etc.).

EDC data will be collected and stored until re-examination results are provided from the local regulatory authority, MHLW (Ministry of Health, Labour and Welfare), and there is reconfirmation of the clinical usefulness of the study drugs. There will be restricted access to the EDC data, and only study personnel with assigned user IDs will be able to access the system.

7.4.1 Study Procedures

Patients will be observed from initiation of pembrolizumab plus axitinib until the end of observation due to withdrawal of consent, loss to follow-up, death, or until end of the study period. The study period is intended to extend for up to 9 months after initiation of therapy. Visits will not occur according to a set schedule, and will be driven by clinical management of patients at each site. However, it is expected that site visits will occur approximately every 3 weeks, based on the dosing recommendations for pembrolizumab in the product label.

After the decision by HCP to treat the patients with pembrolizumab in combination with axitinib, patients recruited for the study will consent to study participation, in accordance with local ethics committee requirements. As a general rule, patients should be registered within 14 days from the starting day of the index drugs. Sites will complete and submit a patient

VEAP ID NO: 9069

registration CRF using an electronic data capture (EDC) system, and the CRF will include some baseline information include patient identifier number, gender, year and month of birth or age at the start of treatment, treatment at an inpatient or outpatient facility, starting date of drug administration, and reason for drug use (see Table 1, below). The additional CRFs will be collected and submitted at the end of the 9-month observational period for each patient. Site guidance will be to complete and submit the CRFs within 1 month after the 9-month period of observation, and it is anticipated that an additional 1-2 months will be needed for MAH to query and correct/update entries, as needed (see Figure 1). Training on the EDC data capture system will be performed by the MAH designee (CRO).

After the 9-month period of observation, the CRO will send an email request to the HCP asking him or her to submit the complete CRFs via the EDC system. An email reminder is sent to the site at least once a month until the CRFs are completed and submitted using the EDC system.

Table 1 Schedule for Completion/Submission of Case Report Forms

	Completion and Submission of Registration Forms (guidance is to register	Completion and Submission of Additional Case Report Forms (guidance is to
	patients within 14 days of index date ¹)	complete/submit within one month after the 9-month period of observation)
Name of facility		
Name of department	$\sqrt{}$	
Date of form completion	$\sqrt{}$	
Patient Identification Number	$\sqrt{}$	
Gender	$\sqrt{}$	
Year or Month of Birth, or Age at Start of Treatment	$\sqrt{}$	
Inpatient/Outpatient Category	V	
Starting Date of Drug Administration	V	
Reasons for Drug Use	√	
History of Hypersensitivity to Drug Administration	√	
Additional Exposure Data		$\sqrt{}$
(see Section 7.3.1, above)		
Outcomes Data (see Section 7.3.2, above)		V
Additional Covariate Data		
(see Section 7.3.3, above)		
Outcomes Data (see Section 7.3.2, above)		

¹ index date is date of pembrolizumab plus axitinib

² When hepatic AEs occur, investigators will be instructed to report them via EDC per the AE reporting timelines outlined in Section 9 of this protocol.

VEAP ID NO: 9069

7.5 Study Size

Statistical analyses will be of an explorative and descriptive nature. The study is not aimed to confirm or reject pre-defined hypotheses, and no formal power calculation has been performed.

The goal is to collect complete data on approximately 150 patients, as discussed with the PMDA. With data on 150 patients, some information on treatment patterns, interruption, treatment, and re-administration may be available from this study given what was observed in KN-426 as subsequently noted.

- In KN426, the incidence of patients with hepatic function disorder (adverse events) was 49.4% (212 of 429 patients), of whom the incidence of Grade 3 or higher was 21.2% (91 of 429 patients). If the true incidence rate in this population is the same, a sample size of 150 patients would be sufficient to observe approximately 30 patients with Grade 3 or higher events.
- In KN426, 14.9% (64 of 429), 20.3% (87 of 429), and 11.4% (49 of 429) of patients, respectively, experienced hepatic adverse events leading to treatment interruption with drug, axitinib, or both. Therefore, approximately 22 patients, 30 patients, and 17 patients, respectively, would be anticipated to be observed.
- In KN426, 10.0% (43 of 429), 6.8% (29 of 429), and 3.0% (13 of 429), respectively, of patients discontinued drug, axitinib, or both due to hepatic adverse events. Therefore, approximately 15 patients, 10 patients, and 5 patients, respectively, would be anticipated to be observed.
- In KN426, 15.9% (68 of 429) of the patients whose ALT increased to 3 times the upper limit of normal were treated with systemic corticosteroids. Therefore, approximately 24 patients treated with corticosteroids for liver-related adverse events would be anticipated to be observed.
- In addition, 21.4% (92 of 429) of the patients in KN426 who experienced an increase in ALT 3 times the upper limit of normal who were re-administered any investigational drug after recovery. Therefore, re-administration information on approximately 32 patients would be anticipated to be observed.

A sample size of 150 patients would also provide reasonable statistical precision around the estimated risk of grade 3 and 4 AEs in KN426 (see Table 2, below)

VEAP ID NO: 9069

Table 2 Half width of 95% CI estimates for AE assumptions and proposed sample size for study

N	A.E. Ingidanaa Data (0/)	95% Confider	nce Interval (%)
IN	AE Incidence Rate (%)	Lower bound	Upper bound
100	10	4.9%	17.6%
100	20	12.7%	29.2%
100	30	21.2%	40.0%
150	10	5.7%	16.0%
150	20	13.9%	27.3%
150	30	22.8%	38.0%
180	10	6.0%	15.3%
180	20	14.4%	26.6%
180	30	23.4%	37.3%
200	10	6.2%	15.0%
200	20	14.7%	26.2%
200	30	23.7%	36.9%

AE= adverse event; CI= confidence interval; CI based on Binomial (Clopper-Pearson) 'exact' method based on the beta distribution

7.6 Data Management

All data will be collected, processed, and stored centrally via an electronic data capture (EDC) system

The EDC system is a secure web application for building and managing online databases. It provides secure access for sites, with an audit trail to track the history of data entry and revisions. The database for the study will be developed with built into logic and consistency checks, intended to minimize data errors at the point of entry. As received, the MAH designee will review the CRF entries and, as needed, the clinical site may be asked by the designee to add, correct, or confirm conflicting or unclear entries through the EDC system.

7.7 Data Analysis

Statistical analyses will be of an explorative and descriptive nature. Descriptive statistics will be reported including measures of central tendency and dispersion (mean, median, standard deviation, range) for continuous variables and frequency and percentages for categorical scale variables. Comparison of characteristics in subgroups will be performed using Chi-square test, or Fisher's exact test for categorical/binary variables, and Student's t-test for continuous data. Other test statistics may be used, as relevant, depending on the data distributions and normality assumptions.

Statistical analyses will be performed using SAS software (version 9.3 or higher) or other validated statistical software as required. Subgroup analyses stratified by prognostic /

VEAP ID NO: 9069

predictive factors may be explored. Details of the statistical analyses including handling of missing data, and sensitivity analyses, will be included in a separate Statistical Analysis Plan (SAP), and mock data tables, that will be finalized prior to database lock. A final report will be generated for this study.

7.8 Quality Control

Participating medical institutions sign contracts stating that the HCPs will conduct the survey based on the protocol and physicians guide, and in compliance with governing laws and regulations including the GPSP. The site contract stipulates that quality control procedures will be followed for the conduct of the study.

All parties also agree to ensuring all existing and new study personnel are appropriately trained to ensure the study is conducted and data are generated, documented, and reported in compliance with the protocol, and all applicable federal, state, and local laws, rules and regulations. All parties should maintain transparency and open communication in order to effectively manage the study and proactively mitigate any risks.

7.9 Limitations of the Research Methods

Given its observational nature, the study is prone to potential forms of bias including, for example selection bias, surveillance bias and information bias. Also, the results may not be generalizable to patients treated within other countries and healthcare systems.

A potential form of bias for this study is selection bias, which occurs when patients in the study differ systematically from the population of interest (patients with radically unresectable or metastatic RCC), limiting the generalizability of results to the broader patient population. For this study, there will likely be some degree of selection bias given the index drugs are commercially available and patient consent to study participation will be necessary. The descriptive baseline demographic and medical history for patients included in this study can be qualitatively compared with other trial and realworld evidence studies of patients with advanced RCC to help put these results into context.

With the introduction of new drugs for a given indication, there is also the potential for another form of selection or allocation bias due to the channeling of newly marketed drugs to more severe cases. This may result in channeling bias with a higher risk of adverse events being reported than would be expected for the general population of patients receiving drug. Comparison of baseline characteristics with other general RCC study populations may also help in identifying the potential degree of channeling bias.

The study may also suffer from bias due to increased surveillance, screening or testing of the outcome or associated symptoms given the noted primary objective of the study. One way to help with interpretation of results in this instance would be to include a comparator drug to allow for the assessment of relative risk. However, inclusion of a comparator group is not possible in this study given the DURS design and limitations imposed by governing ordinances (GPSP) for these surveillance studies. It is also likely that the outcomes reported for the study

Product: MK-3475 23

Protocol/Amendment No.: 3475-A97/000

VEAP ID NO: 9069

are generally more severe in nature, than otherwise would be observed and potentially attributable to treatment. This bias is hard to address given the observational study design, and is a notable limitation of this study.

The study also is prone to information bias due to missing data, misclassification errors, or transcription errors. For this study, quality control and data handling procedures will be implemented to help mitigate this potential form of bias. Given the inability to perform source data verification, this bias is also another notable limitation of this study.

Given the potential forms of bias noted for this study, the results should be very cautiously interpreted and cannot, given the current design possible with the governing Japan ministerial ordinance (GPSP), serve as the basis for assessing causality of reported hepatic disorders.

8 PROTECTION OF HUMAN SUBJECTS

8.1 Informed Consent

The physician in charge shall explain the purpose of the survey, the information collected through the survey and the method for using the survey results (e.g., presentation at scientific meetings, manuscript publication). Consent must be documented by the subject's dated signature or by the subject's legally acceptable representative's dated signature on a consent form along with the dated signature of the person conducting the consent discussion. A copy of the information consent form, signed and dated, will be given to the patient or legally acceptable representative prior to participation in the study.

Informed consent requirements will adhere to IRB/ERC requirements, applicable laws and regulations.

9 MANAGEMENT AND REPORTING OF ADVERSE EVENTS/ADVERSE REACTIONS

Adverse Event (AE) Reporting Language for Non-Interventional Study Protocols

Introduction

This is a primary data collection non-interventional study being conducted within routine medical practice. All direction for medication usage is at the discretion of a physician in accordance with usual medical practice. No administration of any therapeutic or prophylactic agent is required in this protocol, and there are no procedures required as part of this protocol.

9.1 Adverse Event Reporting

The following guidelines for adverse event (AE) apply to the reporting of hepatic events, as described in this protocol. The reporting for product quality complaints and non-hepatic adverse events will follow local reporting guidelines.

VEAP ID NO: 9069

9.1.1 INVESTIGATOR RESPOSIBILITY

If hepatic adverse events (AEs) are identified following use of pembrolizumab, then the AE* must be reported according to Table 3.

*For the purposes of this protocol, the term "AE" collectively refers to the following reportable events (refer to section 9.2 for definitions):

- Serious adverse events (SAEs), including death due to any cause
- Non-serious adverse reactions (NSARs)
- Study-specific Health Outcomes of Interest (HOIs) that meet criteria for SAE/NSAR or special situation

Hepatic AEs will be captured using the eDC for each patient and reported according to Table 3.

The investigator must evaluate each SAE for causality and record causality on the CRF for each SAE and NSAR reported.

Table 3 AE Reporting Timeframes and Process for Investigators and Supplier

AEs	INVESTIGATOR TIMEFRAMES	SUPPLIER TIMEFRAMES
	Investigator to Supplier [1], [2]	Supplier to MSD KK [3]
Hepatic SAE regardless of causality (including study-specific HOIs that meet criteria for SAE)	1	1 BD/3 CD from time of receipt from investigator
Hepatic NSAR (including study-specific HOIs that meet criteria for NSAR)	10 CD from receipt	1 BD/3 CD from time of receipt from investigator

Follow-up to any AE-submit using above timeframes

BD-Business Day; CD-Calendar Day

- [1] Investigator to Supplier: Hepatic AEs for Merck study product are submitted to Supplier via eDC
- [2] Investigator enters hepatic AEs for Merck study product into study database for tabulation in study report
- [3] Supplier to MSD KK: Supplier submits hepatic AEs for Merck study product to MSD KK using EngageZone for reporting to worldwide regulatory agencies as appropriate

Submitting Hepatic AEs to Local PV

Submitting Hepatic AEs to Local PV Japan: All hepatic AEs must be submitted to Local PV using EngageZone as described in the data management procedure for Supplier.

VEAP ID NO: 9069

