6.1 Primary Objectives

Among Japanese patients with radically unresectable or metastatic RCC who receive treatment with pembrolizumab in combination with axitinib, to describe the proportion of patients with hepatic disorders, including clinical events and/or laboratory elevations with or without hepatic dysfunction.

Protocol/Amendment No.: 3475-A97/000

VEAP ID NO: 9069

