6.2 Secondary Objectives

Among the overall population:

1. To describe the demographic and baseline medical history;

- 2. To describe baseline medication use;
- 3. To describe the proportion of patients who discontinue one or both drugs due to hepatotoxicity (overall, serious and grade 3 or higher), including clinical events and/or laboratory elevations, and time to discontinuation;
- 4. To describe the proportion of patients with one or both drugs interrupted due to hepatotoxicity (overall, serious and grade 3 or higher), including clinical events and/or laboratory elevations, time to interruption, and time to resumption of the index drug (s);
- 5. To describe the proportion of patients with a dose reduction for one or both drugs due to hepatotoxicity (overall, serious and grade 3 or higher), including clinical events and/or laboratory elevations, and time to dose reduction;

Among patients with hepatic disorders (overall, serious and grade 3 or higher), including clinical events and/or laboratory elevations:

- 6. To describe the demographic and baseline medical history;
- 7. To describe baseline and concomitant medication use;
- 8. To describe the proportion of patients with hepatic AEs that resolve;
- 9. To describe the proportion of patients using systemic corticoid steroids and other treatments;
- 10. To describe the time from initiation of pembrolizumab in combination with axitinib to onset of hepatic AEs;
- 11. To summarize the type of hepatic disorders.

Subgroup analyses will be conducted for drug-related adverse events, based on investigator assessed causality.

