9.2.1 Adverse Event (AE)

Any untoward medical occurrence in a patient or clinical investigation subject administered sponsor's product and which does not necessarily have to have a causal relationship with this product. An adverse event can therefore be any unfavourable and unintended sign (including an abnormal laboratory finding, for example), symptom, or disease temporally associated with the use of the product, whether or not considered related to the product. Any worsening (i.e., any clinically significant adverse change in frequency and/or intensity) of a preexisting condition that is temporally associated with the use of the product, is also an adverse event.

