9.2.7 Causality Assessment

A causality assessment is the determination of whether or not there is at least a reasonable possibility that a product caused the adverse event. Causality must be recorded on the AE form by the investigator for each reported event in relationship to a Sponsor's product.

Primary Data Collection

The assessment of causality is to be determined by an investigator who is a qualified healthcare professional according to his/her best clinical judgment. Use the following criteria as guidance (not all criteria must be present to be indicative of causality to a Sponsor's product): There is evidence of exposure to the Sponsor's product; the temporal sequence of the AE onset relative to the administration of the Sponsor's product is reasonable; the AE is more likely explained by the Sponsor's product than by another cause.

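### Section 9.1.1 restricts non-serious AEs to adverse reactions and feeds the study report, which conflicts with the all-causality primary outcome and leaves open whether unrelated non-serious hepatic events are counted

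*Protocol*

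**What the plan says.** **Outcome sections of the Protocol.** Section 6.1 sets the primary objective: "to describe the proportion of patients with hepatic disorders, including clinical events and/or laboratory elevations with or without hepatic dysfunction". It has no seriousness or causality condition. Section 6.2 adds: "Subgroup analyses will be conducted for drug-related adverse events, based on investigator assessed causality". Section 7.3.2 names hepatic clinical events and liver-test changes as the health outcomes of interest and lists among the data items the "causal relationship of pembrolizumab and/or axitinib as assessed by the local HCP". Section 9.2.1 defines an adverse event as an untoward occurrence "whether or not considered related to the product".

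**Reporting section.** Section 9.1.1 says that, for the purposes of the protocol, the term AE "collectively refers to the following reportable events (refer to section 9.2 for definitions". The list has three items: serious adverse events (SAEs), non-serious adverse reactions (NSARs), and HOIs that meet SAE or NSAR criteria or are a special situation. Section 9.2.2 makes a causal relationship part of what an adverse reaction is. Table 3 has one row for hepatic SAEs regardless of causality and one for hepatic NSARs. Its footnote [2] reads: "Investigator enters hepatic AEs for Merck study product into study database for tabulation in study report". Section 9.1.1 asks for causality on the CRF for each SAE and NSAR reported. Section 9.2.7 says: "Causality must be recorded on the AE form by the investigator for each reported event", and ties that judgement to a product of the sponsor.

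**The concern.** The 9.1.1 definition is worded for the protocol as a whole, and footnote [2] carries it beyond pharmacovigilance into the tables of the study report. Under that definition a non-serious hepatic event that the investigator considers unrelated is not an AE, unless it is a special situation, and Table 3 has no row for it. A site working from Section 9 could reasonably not enter a mild transaminase rise that it puts down to liver metastases or viral hepatitis. A site working from Section 7.3.2 would enter it.

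At stake is the numerator of the primary proportion. Under-entry would lower the estimate, could differ between sites, and would bring the drug-related subgroup closer to the total. It would also weaken comparison with the KN426 adverse-event figures on which Section 7.5 plans. Recovery is unlikely: Sections 7.3.2 and 7.4 rule out source data verification, and reconciliation under Section 9.3 is aimed at reportable AEs. No analysis plan can restore events that were never entered.

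**Working it through.** **1. The two rules side by side, for a non-serious hepatic event judged unrelated**

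| Protocol section | Is the event collected or counted? |
|---|---|
| 6.1 | Yes: no causality condition |
| 6.2 | Yes by implication: a drug-related subgroup needs a wider total |
| 7.3.2 | Yes: causality is a data item, not an entry condition |
| 9.2.1 | Yes: an AE regardless of relatedness |
| 9.2.5 | Yes by implication: SAE/NSAR collection is additional to HOI collection |
| 7.4.1 and Table 1 | Yes by implication: outcomes data go on the CRF after the 9 months |
| 9.1.1, definition of AE | No, unless a special situation |
| 9.1.1, Table 3 rows | No row for it |
| 9.1.1, Table 3 footnote [2] | Tabulates hepatic AEs, a term that 9.1.1 has just narrowed |

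The HOI item in the 9.1.1 list does not bring the event back, because it too requires SAE or NSAR criteria or a special situation. No sentence says which rule feeds the primary proportion.

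**2. The plan's own figures.** From Section 7.5, 212/429 = 49.4% with any hepatic AE and 91/429 = 21.2% with Grade 3 or higher. Both reproduce. 150 × 91/429 = 31.8, in line with the stated approximate 30. The Table 2 interval for N = 150 at 20% (13.9% to 27.3%) reproduces with the Clopper-Pearson method. None of these figures is disputed.

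**3. How much of the numerator the conflict touches.** Section 5 gives 35 KN426 patients with serious hepatic AEs. Assume that they are among the 212.

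- Non-serious only: 212 − 35 = 177.
- Share of affected patients: 177/212 = 83%. Share of treated patients: 177/429 = 41.3%.
- Scaled to 150 patients: 150 × 212/429 = 74.1 affected, of whom 150 × 177/429 = 61.9 have only non-serious events.

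**4. Illustration.** Let f be the share of the 177 judged unrelated and not entered. The documents give no value for f, so it is an assumption. Observed proportion = (212 − 177f)/429.

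| f | Observed proportion | Patients missed per 150 |
|---|---|---|
| 0% | 212/429 = 49.4% | 0 |
| 10% | 194.3/429 = 45.3% | 6.2 |
| 20% | 176.6/429 = 41.2% | 12.4 |
| 30% | 158.9/429 = 37.0% | 18.6 |

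For scale, the exact 95% interval for 74 of 150 is 41.1% to 57.6%, a half-width of (57.6 − 41.1)/2, or about 8 points. A share of 20% would shift the estimate by about the same amount.

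**5. A limit on the scale.** Section 7.1 places 15 + 8 = 23 of the 212 onsets after month 9. Counting only the first 9 months gives 189/429 = 44.1%, or 150 × 189/429 = 66 patients. The illustration keeps the 49.4% of Section 7.5. The documents do not split serious cases by period.

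**The case against.** The strongest reply is that Section 9 is a reporting layer and that Section 7.3.2 defines the outcome. Section 9.1 introduces its guidance as applying to reporting, Table 3 is about timeframes, and Section 7.3.1 distinguishes the CRF completed at 9 months from the minimal information sent when an event occurs. Section 9.2.5 says that SAE/NSAR collection comes on top of HOI collection, so a non-serious unrelated event remains an HOI for the outcomes CRF. The wording of footnote [2] does not say related to the product. The threshold for an adverse reaction is only a reasonable possibility, so the share judged unrelated may be small.

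Most of this stands. A reader might infer that the protocol removes such events from the primary outcome, so that the numerator becomes serious events plus reactions to pembrolizumab. The documents do not support that: a route without a causality filter exists, and no rule of exclusion is stated.

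A reader might also infer that events attributed to axitinib alone are lost. That too is only an inference, from the references to pembrolizumab, to the Merck study product and to a product of the sponsor. The documents do not say whether axitinib counts as one, Section 7.3.2 records causality for either drug, and under Section 7.2.1 enrolled patients have received both.

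The reply does not remove the conflict. The 9.1.1 definition is not limited to reporting, footnote [2] concerns study tables, and Section 7.3.1 and Table 1 send sites to Section 9 when hepatic events occur.

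**Conclusion.** The protocol holds two collection rules for non-serious hepatic events judged unrelated and does not say which one governs the primary numerator. Such events may be left out; it is not established that they will be. The conflict bears on the events that make up most of the expected numerator: 177 of 212 affected KN426 patients (83%), if the 35 serious cases lie within the 212. The fall from 49.4% to between 45.3% and 37.0% is an illustration. It needs an assumed unrelated share of 10% to 30%, and it needs the outcomes CRF to recover none of those events. It is not a forecast. The inconsistency is still worth removing before sites enter data, because events never entered cannot be restored at analysis and the repair costs almost nothing.

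**What to change.** In Section 9.1.1 and in footnote [2] of Table 3, state that the SAE/NSAR list governs only expedited reporting timeframes. State also that every hepatic AE under Sections 7.3.2 and 9.2.1, whatever its seriousness or its causality to either drug, is entered in the outcomes CRF and counted in the primary proportion. Align the causality wording of Sections 9.1.1 and 9.2.7 with Section 7.3.2, so that causality to pembrolizumab and to axitinib is recorded for every hepatic AE and not only for SAEs and NSARs.

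The cost is a protocol wording change, at most one further causality field per event, and slightly more entry of non-serious events by sites. Sample size and reporting timeframes do not change.
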